## 1. Background Information

1.1 Name, Description and Intended Use of the Experimental Material Xerostomia is a subjective sensation of dryness of the mouth. Dry mouth can be a symptom or a side effect of other conditions (e.g., diabetes, hypertension, Sjögren's syndrome, stroke). It is also a common side effect of many prescription and nonprescription drugs; including drugs used to treat hypertension, depression, anxiety, allergies, and colds (decongestants and antihistamines). Mouth dryness is commonly associated with oral symptoms such as taste disturbances, bad breath and painful mouth ulcers. Dry mouth can also affect oral functions such as speech, chewing, and swallowing. 1,2

Management includes symptomatic relief and prevention or correction of the sequelae of saliva hypofunction, and treatment of any underlying disease. Adequate hydration of the oral tissues (frequent sips of water) is the standard treatment of xerostomia. Several over-the-counter products (e.g., Biotène®) are also available for treating dry mouth symptoms; however, data collected during 3M-hosted focus groups and voice of customer activities indicated that there continues to be an increasing demand for effective dry-mouth relief products. For this reason, 3M's Oral Care Solutions Division plans to expand their prevention portfolio and has been developing an oral spray solution, which is intended to be used to relieve dry mouth symptoms in persons with Xerostomia.

The purpose of this clinical trial is to evaluate and validate the performance of the experimental mouth spray when used by persons with mild to severe dry mouth symptoms. This study is designed to gather data from these individuals regarding their opinions about the product's performance, mouth-feel qualities, and user's willingness to purchase the product when it becomes commercially available.

We hypothesize that the use of 3MTM Experimental Dry Mouth Moisturizing Spray will be non-inferior to Biotène (GSK) in alleviating dry mouth symptoms.

1.2 Summary of Previous Studies

Page 6 of 36 Status: Release

Version: 3 Issue Date: 07/11/2019 03:08:44 PM CDT

[name]

To determine the preliminary flavor selections for the mouth spray, a food product development and research company (Merlin Company, Plymouth, MN) was employed. They helped in the development of the flavored formulations and conducted various taste panel evaluations with professional taste testers to select and optimize the flavored formulations.

Subsequent to Merlin's evaluators making their favorite flavor choices it was necessary to confirm the flavored formulations in a xerostomia population. Clinical trials were conducted

in healthy volunteers, with self-reported moderate to severe dry mouth, to test the prototype formulations. Two clinical trials were conducted:

- The first study was based solely on spoon delivery of 4 individual prototype formulations to gather taste/flavor preferences to narrow down the flavor options for the final product flavor. The formulations were compared to 2 commercial dry mouth spray formulations.
- The second study was conducted using a spray delivery system to identify the final flavors and to gather preliminary data for immediate dry mouth relief, mouth feel of formulation, and usability compared to Biotène.

# 1.3 Risk/Benefit Summary

#### Risks:

3MTM Dry Mouth Moisturizing Spray is a surface device with limited contact duration per use. As it will be used by subjects with mild to severe xerostomia, some degree of contact on breached or compromised oral mucosa is expected. Therefore, the relevant ISO 10993, ISO 7405, USFDA, and Japan medical device evaluation guidance were used in establishing the study design. Subject with breached or compromised oral surfaces will evaluate the product for >30 days.

A Diplomate of the American Board of Toxicology has assessed the safety of the experimental sample, 3MTM Dry Mouth Moisturizing Spray. Standard risk assessment techniques and consideration of internationally recognized guidelines were used in this evaluation. The experimental sample, 3MTM Dry Mouth Moisturizing Spray is safe for human use in this clinical evaluation based on the following considerations:

Page 7 of 36 Status: Release

Version: 3

Issue Date: 07/11/2019 03:08:44 PM CDT

#### [name]

- 1) All of the ingredients in the product are used in food; and
- 2) A review of the product ingredient hazards in relation to the exposure during the clinical trial

This prototypic device 3MTM Dry Mouth Moisturizing Spray is associated with minimum risks.

#### **Risk Minimization**

Efforts to minimize risks to study subjects will be made with the following approaches:

- Compliance with ISO 10993
- Selection of investigators who are experienced dental clinicians
- Clearly defined inclusion and exclusion criteria will be used to ensure only appropriate subjects are enrolled
- Ensuring that treatment and follow-up of subjects is consistent with current dental practice
- Monitoring of investigational sites and patients
- Review of reported Adverse Events

Based on the biocompatibility and a general risk review, the possible side effects of using the experimental device include:

- Potential stinging or burning sensations associated with the product
- Sloughing of the superficial soft tissues in the oral cavity such as the inside surface of the cheeks
- Paresthesia (local numbing for a short period of time)
- Soft tissue erythema and edema
- The product could accidentally be splashed into the eye and minor, limited irritation may occur
- Allergic reaction to the product

Benefits: There may be no direct benefits to the participants in this study. However, information obtained in this investigation may benefit others in the future.

# 1.4 Investigational Material Application

Experimental material will be dispensed by the subject to their own mouth by using a spray bottle to deliver the oil-in-water emulsion into the mouth.

## 1.5 GCP and Regulatory Requirements

The 3MTM Dry Mouth Moisturizing Spray is a medical device (unclassified). 3M Company (Maplewood, MN) has determined this product is a non-significant risk

Page 8 of 36 Status: Release

Version: 3

Issue Date: 07/11/2019 03:08:44 PM CDT

#### [name]

device, based on biocompatibility testing and the 2 taste studies conducted on 3M Healthy Volunteers, which had no adverse events reported. This study will be conducted in compliance with this protocol and GCP including 45 CFR 160 & 164 (Authorization for Use/Disclosure of PHI),21 CFR 50 (Informed Consent) and 56 (IRBs). The experimental device will be used in a manner consistent with its intended use, and abbreviated CFR 21 FDA §812.2 regulation applies. The device will be registered with the FDA as an unclassified medical device in 2020, subject to 510(k) regulatory pathway based on clearance. It is similar to a previously registered predicate medical device called Biotène® Moisturizing Mouth Spray (510(k) number K123731, K103745).

Prior to FDA approval, a Human Subjects' Protection Board (IRB) serves as a surrogate to the FDA in making a nonsignificant risk determination for review, approval, and continuing review in device-related studies.

A non-significant risk device study may start at the institution as soon as the IRB reviews and approves the study. Progress reports or final reports to FDA and an IDE application to the FDA are not required.

### 1.6 Study Population

Adults that meet the inclusion/exclusion criteria.

## 2. Study Objectives and Purpose

The purpose of this study is to investigate the efficacy of 3MTM Dry Mouth Moisturizing Spray to reduce symptoms of dry mouth for up to 4 hours and after 7 days of use. In addition, this study aims to support comparative claims.

# 3. Study Design

## 3.1 Study Type

The proposed study will be a controlled randomized cross-over design. This study will compare 3MTM Dry Mouth Moisturizing Spray to commercialized device (active control) and water (inactive control) to determine the effect and changes in the effect over time, in subjects experiencing dry mouth symptoms.

## 3.2 Primary and Secondary Endpoints

The primary endpoint of this study is reduction in mouth dryness at 15 minutes after 1 dose of 3MTM Dry Mouth Moisturizing Spray.

We hypothesize that the use of 3MTM Dry Mouth Moisturizing Spray will be non-inferior to GSK Biotène® Moisturizing Mouth Spray (Biotene) in alleviating mouth

Page 9 of 36 Status: Release

Version: 3 Issue Date: 07/11/2019 03:08:44 PM CDT

[name]

dryness as assessed by the Visual Analog Scale for the duration of 15 minutes after 1 dose.

The secondary endpoints are to:

- Mouth dryness evaluated using a Visual Analog Scale, at 5-, 30-, 60-, 120and 240-minutes post 1 dose of use to determine whether 3MTM Dry Mouth Moisturizing Spray is equally effective to the prototype Biotène® control.
- Evaluate the clinical safety of the 3M Dry Mouth Moisturizing Spray.
- Determine product usability, acceptability and preference using patient questionnaires.
- Compare 3MTM Dry Mouth Moisturizing Spray to Biotene® and water.

## 3.3 Randomization and Blinding

All subjects completing the wash-in procedures and meeting inclusion/exclusion criteria will undergo a pre-study 5-hour visit (the day before randomization) to assess the effect of water on their dry mouth symptoms. The subjects will return the next day for confirmation that inclusion/exclusion criteria and the wash-in procedures continue to be met or followed. Eligible subjects will be randomized at this baseline visit in a 1:1 ratio to one of two treatment orders: A->B (AB) or B->A (BA). The order of product usage will be assigned in sealed envelopes created from a randomization schedule generated by the study statistician.

Due to the obvious differences in products and the dispensing spray bottles, blinding of subject to treatment order will not be possible. In addition, no attempt will be made to blind subjects when given a single dose of water the day before randomization.

All clinical oral examinations performed post-randomization will be conducted with the evaluator blinded to subject's product use assignment. Subjects will be instructed to avoid discussing their assigned product with the evaluator.

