#### [name]

## 3.4.1 Investigational Material Labeling

3M will label, package and ship the study materials to the research facility. Each experimental material will be labeled with the following minimum information:

For use in Study EM-11-050038 only 3M Health Care, [name] Identifying lot or control number Study Material name or code designation: Quantity of contents

Expiration date:

"Use as directed"

Storage conditions: Store at room temperature.

If you have questions, call [contact].

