## 3.4.2 Other Material Labeling

Biotene® is a commercially available product. It will be over labeled with the following:

For use in Study EM-11-050038 only 3M Health Care, [name] Identifying lot or control number Study Material name or code designation: Quantity of contents Expiration date: "Use as directed"

Storage conditions: Store at room temperature.

If you have questions, call [contact].

Bottled water will be labeled with Sample C.

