## 3.8 Randomization and Blinding

The cross-over order of treatments will be assigned using sealed randomization envelopes. Order assigned will be either A->B (AB) or B->A (BA). The Investigator or their designated staff member is responsible to assure that the study randomization is followed. Subjects randomized will have their data and records numbered with the assigned numbers 001 to 040. Study treatment materials will be labeled with the appropriate codes. The 3M study monitor must be notified within 24 hours of any emergency deviation from protocol related to randomization errors.

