## Primary endpoint

The primary endpoint is relief of dry mouth, it will be scored using the Visual Analog Scale (VAS) - 10 cm long where the subject will score their mouth dryness. The anchor points of the scale are 0 represents "normal" (i.e., no dry mouth symptoms), and 10 representing "the worst imaginable" dry mouth symptoms.

Page 25 of 36 Status: Release

Version: 3

Issue Date: 07/11/2019 03:08:44 PM CDT

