#### 8.2 Statistical Methods

The primary endpoint will be the paired-difference in VAS scores between experimental and active control product after 15 minutes of the first dose on the first day of the treatment period.

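### Subjects rate the primary outcome themselves, and the labelling rules do not ensure that they are kept from knowing which spray is the sponsor's and which is the market brand

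*Combined protocol and SAP*

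**What the plan says.** Section 6.2 (Primary endpoint) defines the outcome as a visual analogue scale "10 cm long where the subject will score their mouth dryness". Section 8.2 compares the two sprays "after 15 minutes of the first dose on the first day of the treatment period". Section 8.2.1 tests both non-inferiority and superiority, and Section 2 says the study is meant to support comparative claims.

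On masking, Section 3.3 states: "Due to the obvious differences in products and the dispensing spray bottles, blinding of subject to treatment order will not be possible". The same section protects the examiner: "All clinical oral examinations performed post-randomization will be conducted with the evaluator blinded to subject's product use assignment".

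On labelling, Section 3.4.1 lists, among the minimum items on the experimental spray, "Study Material name or code designation". Section 3.4.2 says of the control: "Biotene® is a commercially available product. It will be over labeled with the following", followed by the same study text, which includes the sponsor's name. The water is labelled Sample C. Section 3.8 adds: "Study treatment materials will be labeled with the appropriate codes".

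**The concern.** Section 3.3 treats two things as one. Different bottles, taste and texture mean that a subject will notice that the Period 2 spray is not the Period 1 spray. They do not mean that the subject must know which of the two is the new product. Concealing identity is a separate safeguard, and Section 3.3 does not discuss it.

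Expectation about a known brand or a new product acts directly on a self-rating. The cross-over does not remove it. Such a bias belongs to the product, so it has the same sign in the AB and BA sequences and passes straight into the A minus B estimate. The VAS at the other time points, the attribute scores and the acceptability and preference questionnaires are exposed in the same way. A comparative claim resting on these data would be open to the question of whether subjects rated the spray or the name.

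**Working it through.** **1. What the text does and does not secure**

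| Safeguard | What the documents provide | What is left open |
|---|---|---|
| Coded label | Section 3.8 plans codes; the water is Sample C (3.4.2) | 3.4.1 and 3.4.2 accept a name in place of a code |
| Brand covered | Control is over-labelled with the same study text (3.4.2) | No requirement that the over-label hides the brand; nothing on covering artwork on either bottle |
| Staff silence | Subjects are told not to discuss their product with the evaluator (3.3) | No visible instruction that staff withhold product identity from subjects |

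The consent pages and the Appendix B figures cannot be seen, so what subjects are told there is unknown.

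**2. The plan's own figure**

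Inputs from Section 8.3: margin 1.5, expected difference 0.5, SD of differences 1.5, one-sided alpha 0.01, n = 33.

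- Standard error = 1.5/√33 = 0.261.
- Non-centrality = (1.5 − 0.5)/0.261 = 3.83.
- Power from the non-central t with 32 df = 0.910, against the stated 90%.
- 33 is the smallest n that reaches 90%.
- 33/0.85 = 38.8, so 39 against the stated 40.

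The sample size is sound and is not part of this point.

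**3. Effect of an assumed bias on the error rate**

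Section 8.2.1 tests at one-sided 0.025. Let b be the amount in cm by which expectation lowers A minus B. The documents give no value, so b is an assumption. At a true difference of 1.5 the mean of the observed differences is 1.5 − b, and the chance of declaring non-inferiority is P(T > critical t), where T is non-central t with non-centrality b/(1.5/√n). A paired t-test stands in for the mixed model.

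| b (cm) | Non-centrality, n = 33 | False non-inferiority, n = 33 | False non-inferiority, n = 40 |
|---|---|---|---|
| 0 | 0 | 2.5% | 2.5% |
| 0.1 | 0.38 | 5.6% | 6.1% |
| 0.25 | 0.96 | 15.1% | 17.6% |
| 0.5 | 1.91 | 45.9% | 53.8% |

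The same percentages are the chance of falsely declaring superiority when the true difference is 0.

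**4. Bias in the other direction**

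If expectation favours the known brand by b, non-centrality at the planned difference of 0.5 becomes (1.0 − b)/(1.5/√n). With n = 33 and one-sided 0.025:

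| b (cm) | Non-centrality | Power |
|---|---|---|
| 0 | 3.83 | 96.0% |
| 0.25 | 2.87 | 79.5% |
| 0.5 | 1.91 | 45.9% |

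**The case against.** The strongest reply is that much of the remedy is already planned. The control is over-labelled with the same text as the experimental spray, both labels carry the sponsor's name, materials are to be coded, and Sample C for water suggests a Sample A/B/C scheme. This stands. A reader might infer that the plan abandoned all concealment, and Sections 3.4.2 and 3.8 do not support that. What remains is a gap in the wording: a name is still allowed, and coverage of the brand is not required.

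Second, what subjects are told may be settled in consent text or instructions that cannot be seen. This also stands, and it limits the point on staff disclosure to the visible text.

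Third, a reader might go further and say that the plan leaves its one blinded efficacy measure, the Challacombe score, unanalysed. Section 8 indeed contains no Challacombe analysis. But Section 6.1 does not list the score as an endpoint, and Section 6.2 uses it for eligibility and severity grouping. It is not the only blinded assessment either, because the oral tissue exam falls under the same rule. It is taken before dosing and at the end of each 7-day period, never after the single dose, so it cannot check the 15-minute result. Several items, such as shortened papillae and cervical caries, are structural, and nothing shows that they respond within 7 days.

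Fourth, the subject keeps the bottle for 7 days, but that bears on the questionnaires rather than on the primary rating, which is made in the clinic 15 minutes after the first dose of each period.

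**Conclusion.** The point holds as a correctable gap. A self-rated primary outcome is collected from subjects declared unblindable, and the labelling rules do not ensure that product identity is concealed, although partial concealment looks feasible.

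The size is conditional. With 33 completers and an SD of 1.5, an assumed shift of 0.25 cm towards the experimental spray gives about 15% false non-inferiority at the margin; 0.5 cm, one third of the margin, gives about 46% (18% and 54% with 40). The same shifts towards the known brand would instead reduce power from 96% to about 80% or 46%.

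A reader might take the larger error rates as a finding that the trial favours the sponsor. The documents do not support that: they give neither the direction nor the magnitude of any bias. The figures show only that the primary test would be sensitive to a modest bias in either direction.

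**What to change.** - **Sections 3.4.1 and 3.4.2:** replace the choice between name and code with a code only (Sample A and Sample B, matching Sample C for water). Require the label to cover brand artwork on both bottles.
- **Section 3.3:** keep the statement that subjects can tell the sprays apart. Add that staff do not disclose which code is the experimental spray until the Visit 6 questionnaires are complete. Check that the consent text and the Appendix B instructions are consistent with this.
- **Optional, Section 8.2.1:** report the blinded Challacombe change over each 7-day period (Visits 3 to 4 and 5 to 6) with the planned cross-over model. Label it exploratory and tie it to the 7-day purpose in Section 2, not to the 15-minute result.

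The cost is slightly more labelling work and a line in the staff script, plus one model on data already collected if the optional analysis is added. Sample size, visits and treatment are unchanged. Some subjects may still recognise the bottle or the taste, so masking would be partial and the report should say so.

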## 3.4 Study Materials and Labeling

3M™ Dry Mouth Moisturizing Spray formula is an oil-in-water emulsion. The oil phase provides comfort to the oral mucosa. The water phase is buffered at a neutral pH using a phosphate buffering system, and is sweetened with non-cariogenic sugars including xylitol, erythritol and sucralose. 3M Dry Mouth Moisturizing Spray will be applied to the oral mucosa as needed for the relief of dry mouth symptoms. Components are of food or compendial grade. The instructions for use are provided as Appendix B.

- Treatment [A]: 3MTM Dry Mouth Moisturizing Spray
- Treatment [B]: Control Biotène® Moisturizing Mouth Spray
- Treatment [C]: Control Bottled water

Page 10 of 36 Status: Release

Version: 3

Issue Date: 07/11/2019 03:08:44 PM CDT

#### [name]

## 3.4.1 Investigational Material Labeling

3M will label, package and ship the study materials to the research facility. Each experimental material will be labeled with the following minimum information:

For use in Study EM-11-050038 only 3M Health Care, [name] Identifying lot or control number Study Material name or code designation: Quantity of contents

Expiration date:

"Use as directed"

Storage conditions: Store at room temperature.

If you have questions, call [contact].

## 3.4.2 Other Material Labeling

Biotene® is a commercially available product. It will be over labeled with the following:

For use in Study EM-11-050038 only 3M Health Care, [name] Identifying lot or control number Study Material name or code designation: Quantity of contents Expiration date: "Use as directed"

Storage conditions: Store at room temperature.

If you have questions, call [contact].

Bottled water will be labeled with Sample C.

## 3.5 Study Duration

The anticipated duration of this clinical study from enrollment of first subject to treatment of final subject is 3- to 6 months.

Each participant's time commitment to this research project will be 90 minutes at first visit (screening and enrollment/start of wash-in). On the 2nd visit (water only evaluation) an Oral Exam and Challacombe assessment will be completed prior to dosing. If the Challacombe score is 0, then the subject will not be enrolled, and the time commitment will be up to 90 minutes. If the Challacombe score is 1 or greater, subject will complete to the 5-hour water-only evaluation. On the 3rd visit (baseline period 1) the Challacombe assessment will be re-checked to ensure it is still ≥1. If

Page 11 of 36 Status: Release

Version: 3

Issue Date: 07/11/2019 03:08:44 PM CDT

#### [name]

the subject still meets all the other inclusion/exclusion criteria, the subjects will be randomized into the treatment phase of the study.

Enrolled subjects will be scheduled for 2 additional 5-hour visits and two 60-minute visits. There is also at least a 2-day wash-in period prior to any sample dosing and at least a 2-day wash-out period between 1st and 2nd study periods. Each individual subject will participate in the study for total time of up to 4 weeks. There is the possibility that a subject may develop a study related adverse event during participation. Should this happen, a detailed description of start date and other pertinent information will be recorded on an adverse event form and the subject's continued participation in the study and treatment will be at the Investigator's discretion.

All subjects experiencing an adverse event will be followed until the adverse event is resolved.

Pre-treatment Phase			Treatment Phase				
Screening	(wash-in period)	Water-only Evaluation	Baseline Period 1	End of Treatment Period 1	(wash-out period)	Baseline Period 2	End of treatment Period 2 (End of study)
Start of		-0					(6
wash-in							
(6	68	-1	0	7		9+	16+
	>=2 days				>= 2 days		

Visit

Description/sub-phase Study Day Length of Time

